9.1 Primary Efficacy

The primary efficacy analyses will be based on the ITT population, unless otherwise specified. Table 5 provides an overview of the planned efficacy analyses.

Table 5 Overview of Planned Primary Efficacy Analyses

Endpoint/Parameter/ Display Type	Absolute						Change from Baseline						
	Stats Analysis		Summary		Individual		Stats Analysis		Summary		Individual		
	T	F	T	F	F	L	T	F	L	T	F	F	L
Overall Survival	X	X				X							
Engraftment (PCR for transduced cells)			X	X	X	X							
WASP Expression			X	X	X	X				X			X
T-Cell function			X	X	X	X				X	X		X
Antigen specific response to vaccinations			X	X		X							
Platelet count, MPV			X	X	X	X				X			X

T = Table, F = Figure, L = Listing

Stats Analysis = Represents TFL related to any formal statistical analyses (i.e. modelling) conducted.

Summary = Represents TF related to any summaries (i.e. descriptive statistics) of the observed raw data.

Individual = Represents FL related to any displays of individual subject observed raw data.

Absolute and change from baseline summaries/listings are combined into a single display.

9.1.1 Overall Survival

Overall survival is defined as the time in days from gene therapy to date of death. Subjects alive at the end of follow-up or having not yet reached the defined follow-up phase will be censored at the latest time point for which vital status information is available. Follow-up will be defined as all data up to the data cut or end of study depending upon availability of data per patient.

The Kaplan-Meier estimate of survival for the entire duration of follow up will be obtained, with 95% confidence interval (CI) if there is any fatal event. The analysis results will be presented in a graph as well as a table. A listing of fatal events will be reported as a safety display.

9.1.2 Engraftment of genetically corrected hematopoietic stem cells in peripheral blood and/or in bone marrow

Adequate engraftment of genetically corrected cells in peripheral blood and/or in bone marrow is defined as ≥ 0.04 VCN/cell in bone marrow CD34 $^{+}$ or ≥ 0.1 VCN/cell in peripheral blood T Lymphocytes CD3 $^{+}$ at 1 year after gene therapy.

Missing PB CD3 $^{+}$ values will be imputed using the mean PB CD4 $^{+}$ and PB CD8 $^{+}$ values obtained from the same sample at that visit. If insufficient data are available to determine an adequate engraftment, the response will be set to missing. This includes two scenarios:

- Neither BM nor PB samples provides data for engraftment assessment;
- Values are below the threshold for the respective sample matrix (BLQ).

A summary table detailing the number and percentage of subjects who present with adequate engraftment at 1 year after gene therapy will be generated, with the 95% CI of the percentage calculated. PCR transduced cell evaluation in BM and PB will be summarised with descriptive statistics and graphs. Time to adequate engraftment will be plotted and listed based on VCN in BM and PB. The percentage of lentiviral vector (LVV) transduced colony forming units (CFU) in bone marrow cells (%LV in BM) will also be tabulated and plotted.

The longitudinal profile of the PCR transduced cell evaluation in BM and PB over time will be presented in a listing and a plot.

A box plot will be created for engraftment (PB CD3⁺ and BM CD34⁺ VCN/cell) by treatment source (BM or PB) at each year post gene therapy.

Scatterplots will be presented of treatment dose (CD34+/kg), busulfan dose (AUC), and age at treatment against engraftment (PB CD3⁺ and BM CD34⁺ VCN/cell) at each year post gene therapy.

Line plots will be created for median VCN/cell over time in both the BM and PB cell lineages.

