5.1.4.1. Natural study termination for a single enrolled patient

The natural study termination, for a single enrolled patient, is when the patient has completed a minimum of 5 years follow up in this study (WAS Pivotal, 201228) and has transitioned and has transitioned to a separate OLTFU study. As part of the OLTFU study, patients will continue to be followed up for a total of 15 years from the date of treatment with gene therapy. Should a patient decide not to consent to participate in the ELTFU nor transition to the OLTFU study, then the subject will be considered to have completed this study and will be transitioned to standard of care according to local practice. This study will be considered to have ended once all subjects have transitioned into the separate OLTFU study or transitioned to standard of care according to local practice.

In addition, the following circumstances are to be considered as natural study termination:

- a) Treatment of the patient with allogeneic hematopoietic stem cell transplantation
- b) Loss to follow up
- c) Death of patient

All patients will be included for evaluation until withdrawal.

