12. STATISTICAL DESIGN

12.1. Protocol modification and stopping rules

As already described in section 8.2 for relevant endpoints, rules for protocol modification and stopping serve as guidelines for discussing the continuation/modification of the study. The rules are defined below.

Protocol modification:

- 2 out of the first 3 patients suffering of prolonged aplasia;
- 2 or more failures of engraftment of transduced cells.

Early Stopping:

- 2 transplant-related deaths;
- 1 malignant proliferation related to gene therapy.

In the interest of the patients' safety, the third patient will be treated when:

- at least 1 of the first 2 patients will achieve hematopoietic recovery;
- at least 60 days after the first treatment.

For the subsequent patients the above rules will be applied.

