7.3 Missing Data

Considering the small sample size of the study, missing data will not be imputed unless otherwise indicated. Missing data will be reported as follows:

- These data will be indicated using a “blank” in subject listing displays. Unless all data for a specific visit are missing in which case the data are excluded from the table.
- Answers such as “Not applicable” and “Not evaluable” are not considered to be missing data and will be displayed as such.

For the evaluation of sustained engraftment, if data on peripheral blood (PB) CD3+ is not available, the missing CD3+ value will be imputed as the average of PB CD4+ and CD8+ values obtained from the same sample at that visit.

Completely missing start or end dates will remain missing, with no imputation applied. Consequently, time to onset and duration of such events will be missing. Partial dates will be displayed as captured in subject listing displays.

Partial dates for adverse events, medical history or concomitant medications records will be imputed for the purpose of assigning phase of onset and in the calculation of duration of adverse events.

The methods for dealing with partial start and stop dates are described below for adverse events and concomitant medications.

The answers to the question “Ongoing?” as recorded on the eCRF pages will also be taken into consideration to determine if the event continued post- gene therapy.

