Subjects will be also stratified according to the severity of thrombocytopenia before gene therapy in 5 groups (A, B, C, D and E) and the subject will be defined as improved if there is a positive shift (an increase in platelet count) from one group to the subsequent as shown in Table 7. If a subject has no values more than 7 days from a platelet infusion then they are imputed as being in group A.

Table 7 Stratification of platelet count according to severity of thrombocytopenia (count $\times 10^9/L$)

A	B	C	D	E
< 20	20 - < 50	50 - < 100	100 - < 150	≥ 150

The percentage of subjects who have improved platelet count over baseline at 1 to 8 years (annually) after gene therapy will be calculated with 95% CI.

The means for absolute values and change from baseline will be calculated with 95% CI each year after gene therapy for platelet count and MPV. There will also be accompanying summary statistics.

At 1-8 years after gene therapy the number of subjects with normal MPV will be summarised. The longitudinal profile over time of platelet count and MPV will be described by means of a listing and a plot. The listing will identify which platelet count data points were within 7 days after a platelet infusion as well as thrombocytopenia severity data.

Shift tables of platelet count (as in Table 7) and MPV compared to baseline will be presented for each year after gene therapy.

Median platelet counts will be summarised by baseline WASP expression (Reduced, Absent, Presence of Revertant (>5%)) by means of a bar graph at each year post gene therapy.

Arithmetic mean (and 95% confidence interval) values of platelet count and MPV data will be plotted over time.

A summary of the number of subjects with platelet infusions per treatment phase (See Table 3) will be presented along with the rate of infusions per year of observation.

A summary of time to discontinuation of sustained platelet infusions will be produced for subjects who no longer need platelet infusions. The cessation of sustained infusions is defined as a period of 3 months post gene therapy without a platelet infusion. The time to discontinuation will be presented in a table and Kaplan Meier plot including median time to discontinuation and 95% confidence interval.

Listings of both platelet infusions and time to platelet infusion discontinuation will also be created.

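### SAP 9.1.2 has no rule for a treated subject who dies or receives allogeneic HSCT before the 1-year visit, and its unstated denominator lets such a subject drop out of the primary engraftment percentage

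*SAP*

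**What the plan says.** - **The missing rule.** SAP 9.1.2 sets adequate engraftment at 1 year as a VCN threshold in marrow CD34+ cells or blood T cells. It then says: "If insufficient data are available to determine an adequate engraftment, the response will be set to missing". The first of its two triggers is: "Neither BM nor PB samples provides data for engraftment assessment".
- **The summary.** "A summary table detailing the number and percentage of subjects who present with adequate engraftment at 1 year after gene therapy will be generated", with a 95% CI. No denominator is given. SAP 9.1 places the analysis on the ITT set, which SAP 7.1 defines as all treated patients with data in the database. SAP 8 says in general terms that percentages of the observed levels are reported.
- **Missing data in general.** SAP 7.3: "missing data will not be imputed unless otherwise indicated".
- **Leaving the study.** Protocol 5.1.4.1 counts as natural study termination "Treatment of the patient with allogeneic hematopoietic stem cell transplantation", and also loss to follow-up and death. Neither it nor Protocol 12.4 says how these count in a responder percentage.
- **Early-termination data.** SAP 5.3.3 assigns these to the next visit scheduled for that assessment. Protocol 8.2.6 asks for end-of-study procedures in withdrawn patients where possible.
- **Platelets.** SAP 9.1.6 has one worst-case rule: "If a subject has no values more than 7 days from a platelet infusion then they are imputed as being in group A". It does not mention death or transplant.

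**The concern.** Death and allogeneic HSCT before 1 year are the two events that most clearly mean the treatment did not deliver sustained engraftment in that patient. A primary responder percentage should have a stated way of counting them. Here the derived response can become missing, and the general conventions allow the percentage to be taken over non-missing responses only.

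The situation is realistic on the documents' own evidence. The early-stopping rule in Protocol 12.1 acts at "2 transplant-related deaths", so one is tolerated. Protocol 2.8.1 reports that one of ten patients in the earlier gammaretroviral WAS trial went on to bone marrow transplant after engraftment failed. An equivalent patient here could disappear from the engraftment endpoint because engraftment failed.

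The percentage will be relied on. The protocol refers to the study as the WAS pivotal trial, and SAP 7.4 ties one interim analysis to the marketing-authorisation database.

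**Working it through.** **1. Plan's own figure.** There is none to reproduce. The 8 patients are a feasibility number (SAP 6), and the study is not powered (SAP 7).

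**2. Which subjects the gap reaches.** The Year 1 window is Day 274 to Day 457 (SAP Table 1).

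- *Death within 180 days* (the period in the stopping rule of Protocol 4.2.1.1). No sample can fall in the Year 1 window. Unless an earlier sample is mapped forward, the response is missing.
- *Allogeneic HSCT before Day 274.* The subject leaves the study. With no mapped sample, the response is missing. Suppose instead, with illustrative dates, that a termination blood sample is taken on Day 195, after the Day 180 visit, and transplant follows on Day 200. Under SAP 5.3.3 the next visit is Year 1. If VCN is at least 0.1 per T cell, the transplanted subject scores as a Year 1 responder. SAP Table 1 would instead place Day 195 in the Day 180 window (Day 137 to 273). The SAP does not say which rule takes precedence.
- *Withdrawal.* The response is not automatically missing. A termination sample may be mapped forward, and a subject leaving after Day 274 can have a true Year 1 value.

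**3. Size.** Inputs are n = 8 (SAP 6), the Wilson interval (SAP 9) and the 95% level (SAP 7). The number k of subjects who die or are transplanted without a Year 1 value is an assumption, shown from 0 to 3. All others respond.

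With p = x/n and z = 1.96, the limits are

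[p + z²/(2n) ± z·√((p(1−p) + z²/(4n))/n)] / (1 + z²/n).

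For 7/7, p = 1 and the lower limit reduces to n/(n + z²) = 7/(7 + 3.84) = 64.6%.

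For 7/8, the centre is (0.875 + 0.240)/1.480 = 0.753. The half-width is 1.96·√((0.109 + 0.120)/8)/1.480 = 0.224. This gives 52.9% to 97.8%.

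| k | Missing left out | Counted as non-response |
|---|---|---|
| 0 | 8/8 = 100% (67.6 to 100) | 8/8 = 100% (67.6 to 100) |
| 1 | 7/7 = 100% (64.6 to 100) | 7/8 = 87.5% (52.9 to 97.8) |
| 2 | 6/6 = 100% (61.0 to 100) | 6/8 = 75.0% (40.9 to 92.9) |
| 3 | 5/5 = 100% (56.6 to 100) | 5/8 = 62.5% (30.6 to 86.3) |

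The gap does not depend on everyone else responding. With one observed non-responder and k = 1, the figures are 6/7 = 85.7% (48.7 to 97.4) and 6/8 = 75.0% (40.9 to 92.9).

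**The case against.** **The denominator may already be all ITT subjects.** Setting a response to missing describes the derived variable, not who is divided by. Over 8 ITT subjects a missing response already counts against the rate and gives 7/8. A reader might infer that the SAP prescribes a survivors-only rate, but it does not. The denominator is open, and the general wording in SAP 8 only leans towards non-missing responses. The ambiguity remains: two analysts could report 100% and 87.5% from the same data.

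**Leavers can have Year 1 data.** A reader might infer that everyone who dies, is transplanted or withdraws gives no sample and is automatically missing. The mapping rule, the end-of-study assessment and the wide Year 1 window contradict this for withdrawals and for some transplants. Mapping does not help a subject who dies without a sample. For a transplanted subject it can turn a pre-transplant value into a response.

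**The platelet endpoint is not without any rule.** Read literally, the group A rule in SAP 9.1.6 could reach a subject with no values at all. Its likely target is transfusion dependence, and the SAP does not say that it covers death or transplant.

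**Deaths are visible elsewhere.** Overall survival is a primary endpoint, and disposition and individual engraftment data are reported. That stands for deaths. Transplants are not events in overall survival, and other displays do not correct the percentage.

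**Counting death as non-response is a choice of estimand.** True: VCN could have been ample before death. In a single-arm responder rate it is nonetheless a widely accepted choice, and the observed-case result can stand beside it. The objection does succeed against giving a dead subject a platelet category in a shift table.

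**The effect is hypothetical and the intervals are nominal.** Both are true. They limit how serious the point is, not whether the rule should be written.

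**Conclusion.** The concern holds as a gap in the SAP. The response is set to missing when no marrow or blood data exist, the denominator is unstated, and no rule covers death or allogeneic HSCT before the visit. One affected subject moves the estimate by 12.5 percentage points (100% to 87.5%) and the lower limit from 64.6% to 52.9%. Two move it by 25 points and the lower limit from 61.0% to 40.9%. These figures assume 8 treated subjects, response in all others, no mapped Year 1 sample for the affected subject, and an analyst who leaves missing responses out. With an all-ITT denominator the shift does not arise, although a forward-mapped pre-transplant sample could still score as a response. The documents do not show that any such subject exists.

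**What to change.** In SAP 9.1.2:

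- State the denominator as all ITT subjects treated long enough before the data cut to have reached the visit.
- Score death or allogeneic HSCT before the visit as non-response, regardless of any earlier sample mapped to Year 1.
- Keep missing only for subjects who are alive and untransplanted without an evaluable sample, and show their number.
- Report the observed-case percentage as a sensitivity analysis.

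In SAP 9.1.6, count subjects who died or were transplanted before the visit as not improved in the yearly platelet responder percentage. Do not assign them a laboratory category in the shift tables.

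While the 9.1.2 paragraph is open, its second trigger should be reviewed too. It sets below-threshold values to missing, including in subjects still on study, and raises a related question about removing failures.

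The cost is SAP wording and one derivation, with no new data. The reported percentage is somewhat less favourable if such a subject exists and unchanged if none does.

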4.3. Efficacy Endpoints

4.3.1. Primary efficacy endpoints

a) Overall survival

From day +1 to 3 years after gene therapy, and then monitored as part of the long-term follow up.

b) Sustained engraftment of genetically corrected hematopoietic stem cells in peripheral blood and/or in bone marrow

Presence of gene corrected cells assessed by quantitative PCR on peripheral blood and bone marrow cells at 1 year after gene therapy. Adequate engraftment is defined as ≥ 0.04 VCN/cell in BM CD34+ (equivalent to 4% assuming a VCN of 1) or ≥ 0.1 VCN/cell in peripheral blood T lymphocytes (equivalent to 10% assuming a VCN of 1).

c) Expression of vector-derived WASP

Presence of detectable vector-derived WASP expression at 1 year after gene therapy by FACS analyses and/or Western Blot.

In case of failure of engraftment of transduced cells in two or more patients, intensification of conditioning dose and increase in the minimal cell dose will be considered after an amendment to the study.

d) Improved T-cell functions

Improvement in in vitro T-cell proliferation upon stimulation with anti-CD3i mAbs at 1, 2, and 3 years after gene therapy as compared to pre-gene therapy values.

e) Antigen-specific responses to vaccinations

- Ability to mount a protective humoral response to nominal antigens, including antibodies to at least 4 out of 5 T cell dependent antigens tested (Tetanus Toxoid, Diphtheria, Hepatitis B, Pertussis, Haemophilus B) measured after the end of the vaccination schedule (foreseen >1 year after gene therapy). In case results are available on $n < 5$ antigens, the rule of at least $n-1$ will be applied for defining success.

- Ability to mount a protective humoral response to unconjugated polysaccharide antigens (Pneumococcus), measured after the end of the vaccination schedule (foreseen >1 year after gene therapy).

- Positive cellular response to Tetanus Toxoid after vaccination, measured by *in vitro* proliferative response >1 year after gene therapy.

f) Improved platelet count and normalization of MPV

Sustained increase in platelet count compared to baseline during the 3 year follow up, analyzing the individual longitudinal profile, according to the planned follow up visit and including platelet counts collected for clinical reasons during follow up (in transfusion independent patients).

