12.4. Efficacy endpoints

Primary efficacy endpoints

Overall survival

The Kaplan-Meier estimate of survival at 3 years from gene therapy will be obtained, with 95% Confidence Intervals, based on deaths by any causes related to disease. Survival will be also monitored as part of the long-term follow up.

Sustained engraftment of genetically corrected haematopoietic stem cells in peripheral blood and/or in bone marrow

The percentage of subjects who present at one year after gene therapy with adequate engraftment defined as $\geq 4\%$ CD34+ in the bone marrow or $\geq 10\%$ in peripheral blood T lymphocytes will be estimated and the 95% Confidence Intervals (CI) of this proportion will also be calculated. The description of the longitudinal profile over time of the percentage of gene corrected cells on both bone marrow and peripheral blood might be included as additional information.

Expression of vector-derived WASP

The percentage of subjects who present at one year after gene therapy with detectable vector-derived WASP expression will be estimated, with 95% CI.

Improved T-cell functions

The mean change between the pre-gene therapy and the 1-year values of in vitro T-cell proliferation upon stimulation with anti-CD3i will be calculated, with 95% CI, if appropriate. The description of the longitudinal profile over time of the levels of the in vitro T-cell proliferation might be included as additional information. The degree of correction (reached at 1, 2 and 3 years from gene therapy) with respect to normal control levels will also be described.

Antigen-specific responses to vaccinations

The percentage of subjects who respond to vaccination (see Section 9.4) performed > 1 year after gene therapy will be estimated, with 95% CI.

Improved platelet count

The percentage of subjects who improved the level of platelet count at 1, 2 and 3 years after gene therapy compared to baseline, shifting from one category to the subsequent as defined in Section 9.5, will be estimated, with 95% CI. The relative mean change in platelet count with respect to pre-gene therapy value will also be given. The description of the longitudinal profile over time of the platelet count might be included as additional information.

Secondary efficacy endpoints

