8.6 Treatment Exposure

Exposure to study medication, which for this study is gene therapy, will be presented for the ITT set.

Exposure will be presented through summary statistics (n, mean, SD, median, min and max) of:

- Total volume infused (mL)
- Total nucleated cells (10^6)
- Number of nucleated cells/kg (10^6 /kg)
- CD34⁺ cells/kg (10^6 /kg)
- Number of CFU-GM (/ 10^6)
- Transduction Efficiency (CFU-C) (%)
- Vector copy number (VCN/cell)

Data on study medication exposure will also be listed. A listing will also be created of the stem cells collected.

9 Efficacy Analyses

As defined in the protocol, confidence intervals for proportions will be calculated according to the Wilson approach ([Brown, 2001](#)):

$$\left(\hat{p} + \frac{z_{\alpha/2}^2}{2n} \pm \frac{z_{\alpha/2} \sqrt{\left(\hat{p}(1 - \hat{p}) + \frac{z_{\alpha/2}^2}{4n} \right)}}{\sqrt{\frac{1 + z_{\alpha/2}^2}{n}}} \right)$$

Where \hat{p} is the proportion with the event, and n is total number and $z_{\alpha/2}$ is the $100 \left(1 - \frac{\alpha}{2}\right)$ percentile of the standard normal distribution. This can be calculated using the CL=WILSON option within the PROC FREQ procedure in SAS.

An exact Poisson procedure will be adopted for deriving CIs for incidence rates using the below formulas:

$$Y_l = \frac{\chi_{2Y, \alpha/2}^2}{2T} \text{ and } Y_u = \frac{\chi_{2(Y+1), 1-\alpha/2}^2}{2T}$$

Where Y is the observed number of events, Y_l and Y_u are the lower and upper confidence limits for Y respectively, $\chi_{\nu, \alpha}^2$ is the chi-squared quantile for the upper tail probability on ν degrees of freedom, and T is the person year time at risk.

Confidence Intervals for the means or mean changes in continuous variables will be derived with standard parametric methods, if appropriate. Otherwise medians with their corresponding confidence intervals will be presented.

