16.2 Efficacy

16.2.1 Tables

Number	Title	Analysis Set
14.2.1.1.1	Summary of Overall Survival	ITT
14.2.1.2.1	Summary of Subjects with Adequate Engraftment Findings Over Time - Bone Marrow CD34+ and Periperal Blood CD3+	ITT
14.2.1.2.2	Summary Statistics of Vector Copy Number Evaluation in BM and PB cells	ITT
14.2.1.2.6	Summary Statistics of Percentage of Lentiviral Vector Transduced-Colony Forming Units in Bone Marrow Cells (%LVV+ CFU in BM) Over Time	ITT
14.2.1.2.12	Summary of Time to Adequate Engraftment	ITT
14.2.1.3.1	Summary Statistics of Cells Expressing WASP Assessed by Flow Cytometry Over Time	ITT
14.2.1.4.1	Summary Statistics of T-Cell Function	ITT
14.2.1.5.1	Summary of Subjects with Positive Antigen-Specific Responses to Vaccinations	ITT
14.2.1.5.2	Summary of Number and Rate of IVIG Treatment Required by Treatment Phase	ITT
14.2.1.5.3	Summary of Time to Cessation of Sustained IVIG Therapy	ITT
14.2.1.6.1	Summary of Subjects with Improved Platelet Count Over Baseline at Each Year Post Gene Therapy	ITT
14.2.1.6.2	Summary Statistics of Platelet Count and MPV Data	ITT
14.2.1.6.3	Summary of Shifts in Categorical Platelet Count Data From Baseline to Each Year Post Gene Therapy	ITT
14.2.1.6.4	Summary of Shifts in MPV From Baseline to Each Year Post Gene Therapy	ITT
14.2.1.6.7	Summary of Number and Rate of Platelet Infusions by Treatment Phase	ITT
14.2.1.6.8	Summary of Time to Cessation of Sustained Platelet Infusion Therapy	ITT
14.2.2.1.1	Summary of Subjects with Adequate Multilineage Engraftment Findings at Each Year Post Gene Therapy	ITT
14.2.2.2.1	Summary of Severe Infections and All Bleeding Events	ITT
14.2.2.2.3	Summary of Number and Rate of Bleeding Events by Treatment Phase and Severity	ITT
14.2.2.2.4	Summary of Number and Rate of Severe Infections Events by Treatment Phase	ITT

14.2.2.2.6	Summary of Number and Rate of Bleeding Events (Defined from Haemorrhages (SMQ)) by Treatment Phase and Severity	ITT
14.2.2.3.1	Summary of Number of Subjects with Positive Autoimmunity Test	ITT
14.2.2.4.1	Eczema Score Shift Table	ITT
14.2.2.5.1	Summary of Social Life Data Over Time	ITT
14.2.2.5.2	Summary Statistics of Lansky/Karnofsky Performance Index	ITT
14.2.2.6.1	Summary of Days and Rate of Hospitalisation by Treatment Phase	ITT
14.2.3.1.1	Summary of Antimicrobial Treatments by ATC Level 1, Preferred Term and Treatment Phase	ITT
14.2.3.1.2	Summary of Number and Rate of Antimicrobial Treatment Required by Treatment Phase	ITT

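### SAP 9.1.2 codes a below-quantification engraftment result at 1 year as missing rather than as non-response, and the denominator of the percentage is not stated

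*SAP*

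**What the plan says.** SAP 9.1.2 defines adequate engraftment at 1 year as at least 0.04 VCN/cell in bone marrow CD34+ cells or at least 0.1 VCN/cell in peripheral blood CD3+ cells. Meeting either cut-off is enough. It then states: "If insufficient data are available to determine an adequate engraftment, the response will be set to missing". Two scenarios are listed under this rule. In the first, neither marrow nor blood yields data. The second is "Values are below the threshold for the respective sample matrix (BLQ").

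The same section asks for the number and percentage of subjects with adequate engraftment at 1 year, with a 95% CI. Protocol 12.4 asks for the same statistic ("The percentage of subjects who present at one year after gene therapy with adequate engraftment defined as" the two cut-offs) and has no rule for BLQ or missing responses.

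On the denominator, SAP 9.1 says "The primary efficacy analyses will be based on the ITT population, unless otherwise specified". The table concerned, 14.2.1.2.1 ("Summary of Subjects with Adequate Engraftment Findings Over Time"), is assigned to the ITT set, which SAP Table 4 defines as all treated patients with data in the clinical database. The Wilson formula at the start of SAP section 9 explains its symbols thus: the estimate "is the proportion with the event, and n is total number".

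SAP 9.2.2 takes its definition of adequate engraftment from 9.1.2 and applies it over the whole follow-up.

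**The concern.** The no-data case has a bullet of its own, so the BLQ bullet must concern samples that were assayed and came back low. Such a result normally says that the patient lies below the cut-off. Coding it as missing removes the clearest failures from the failure category and leaves the milder ones in it.

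Elsewhere the plan treats absence of engraftment at 1 year as something that can be established. Under SAP section 7 and Protocol 12.2, a patient with no transduced cells in blood and marrow at that time is afterwards evaluated for safety only. Such a patient could be missing in the year-1 primary rate and then outside later efficacy evaluation, and so never be counted as an engraftment non-responder.

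At stake are the reported rate and its interval for a primary efficacy endpoint in 8 patients, where one patient is 12.5 percentage points.

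**Working it through.** The documents state no expected engraftment rate or interval, so there is no figure to reproduce. The check has three steps.

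**1. How results are coded.** Inputs: the cut-offs and the two missing-data bullets of SAP 9.1.2. Assumption: the LOQ is at or below 0.04 (marrow) and 0.1 (blood).

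| 1-year result | Coding under SAP 9.1.2 |
|---|---|
| At or above the cut-off in either matrix | Responder |
| Quantifiable in both, below both cut-offs | Non-responder |
| BLQ in both | Missing |
| No data from either | Missing |

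Rows two and three are out of order: the lower result gets the less unfavourable code. If low cell input raised a sample's LOQ above the cut-off, a BLQ result would not decide the response and missing would be reasonable. The bullet is not limited to that case.

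**2. What the documents say about the denominator.**

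- Towards all 8: the ITT set for primary efficacy and for Table 14.2.1.2.1, and the Wilson n described as a total.
- Towards non-missing only: SAP section 8 reports categorical percentages for the levels observed, and SAP 7.3 does not impute missing data unless otherwise indicated. SAP section 9 names PROC FREQ with CL=WILSON, which leaves missing values out unless told otherwise.
- Not available here: the separate shells document to which SAP section 8 defers further detail.

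None of these says what happens to a response that has been set to missing.

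**3. Size if missing responses are dropped.** Inputs: 8 treated patients (Protocol 5.1.3, SAP section 6), Wilson method (Protocol 12.5, SAP section 9), 95% level (SAP section 7). The numbers of BLQ patients are illustrative.

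With r responders and one failure dropped from 8, the rate rises by r/7 − r/8 = r/56. That is 12.5 points for r = 7, 10.7 for r = 6, 8.9 for r = 5 and 7.1 for r = 4. Dropping a failure can never lower the rate.

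The Wilson interval is [p + z²/(2n) ± z√(p(1−p)/n + z²/(4n²))] / (1 + z²/n), with z = 1.960 and z² = 3.8415.

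- 7/8: centre (0.875 + 0.2401)/1.4802 = 0.7533; half-width 1.960 × √(0.01367 + 0.01501)/1.4802 = 0.2242; interval 52.9–97.8%.
- 7/7: the lower limit reduces to n/(n + z²) = 7/10.8415 = 64.6%; the upper limit is 100%.
- 6/6: 6/9.8415 = 61.0%; the upper limit is 100%.
- 6/8 and 6/7 follow from the same formula.

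| Situation among 8 | Missing dropped | All 8 kept |
|---|---|---|
| 1 BLQ failure, 7 responders | 7/7 = 100% (64.6–100) | 7/8 = 87.5% (52.9–97.8) |
| 2 BLQ failures, 6 responders | 6/6 = 100% (61.0–100) | 6/8 = 75.0% (40.9–92.9) |
| 1 BLQ and 1 quantifiable failure, 6 responders | 6/7 = 85.7% (48.7–97.4) | 6/8 = 75.0% (40.9–92.9) |
| No BLQ, 8 responders | 8/8 = 100% (67.6–100) | 8/8 = 100% (67.6–100) |

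**The case against.** **The BLQ bullet sits under a condition.** It illustrates insufficient data, so it can be read as covering only BLQ results that leave the response undecided. That is a possible intention, but the text does not say so. As written, it names BLQ values without qualification.

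**The denominator evidence leans towards all 8.** The ITT wording and the Wilson n favour it, and the shells may settle it. This stands: a reader should not conclude that the plan will inflate the rate. The pointers the other way, including the named SAS procedure, still make exclusion a real possibility, and the SAP should decide it.

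**Little turns on the rate.** The study is unpowered, its intervals are nominal (SAP section 7), and no success threshold is attached to this percentage. Individual VCN profiles and listings and a time-to-engraftment analysis are planned, so a non-engrafter would be visible and a reader could recompute. This limits the consequence to the headline rate and interval.

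Two stronger readings are tempting, and the documents support neither.

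- *The threshold means the 0.04 and 0.1 cut-offs, so every non-responder becomes missing.* The abbreviation BLQ and the reference to the sample matrix are assay language. On that reading, no failure could ever be recorded, and the percentage and interval requested in the same section would be empty.
- *The rule contradicts the protocol's provisions on engraftment failure.* Protocol 12.1 lists "2 or more failures of engraftment of transduced cells", and Protocol 4.3.1 has a provision that begins "In case of failure of engraftment of transduced cells in two or more patients". But 12.1 presents its rules as guidance for discussion, and neither place ties failure to the two cut-offs or to the SAP's response variable. A patient could count there however the table is coded.

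**Conclusion.** The coding rule is wrong as written. Given an LOQ at or below the cut-offs, it labels a measured non-responder as missing, out of line with the plan's own treatment of absent engraftment at 1 year. That assumption must be checked, because the clinical LOQ is not in the documents.

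Whether the reported rate is affected depends on a denominator that the SAP does not state. If missing responses are dropped, one BLQ failure with the rest responding moves the result from 87.5% to 100%, and two move it from 75.0% to 100%. If all ITT subjects stay in, the percentage does not move and the fault is one of labelling. SAP 9.2.2 inherits the rule, so a later loss of engraftment could also be coded missing. The point is worth correcting before the final analysis. It does not undermine the individual data.

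**What to change.** In SAP 9.1.2, and by reference in 9.2.2, replace the BLQ bullet with:

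> A BLQ result from a sample whose LOQ is at or below the cut-off counts as below the cut-off. A subject with evaluable BM CD34+ and PB CD3+ results, neither meeting its cut-off, is a non-responder. Response is missing only if no evaluable result exists (no sample, or LOQ above the cut-off).

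State that the percentage and the Wilson n use all ITT subjects, and report the number missing beside them, so that the observed-case percentage can be worked out. Give the clinical LOQ for each matrix. List the change in SAP section 14. The authors should also confirm that non-response is intended when one matrix is evaluable and low and the other is unavailable; under the last sentence of this text such a subject is not missing.

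Cost: wording, plus the LOQ from the laboratory; no new patient data. The reported rate may be slightly less favourable, and a subject with no evaluable sample stays in the denominator. Final tables may differ from interim tables made under the present rule. On the protocol's planned dates (start April 2010, five years of enrolment), 1-year data probably predate a SAP based on the September 2023 protocol. The entry in section 14 should therefore give the date and reason for the change.
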